APPENDIX E: DEFINITIONS AND ACRONYMS

ADVERSE EVENT (AE)

Any unfavorable and unintended sign (including an abnormal laboratory finding), symptom, or disease temporarily associated with the use of a device, whether or not related to the device.

ANIMAL ORIGIN INFECTIOUS AGENT TRANSMISSION

Infection with any organism not commonly found in human beings which can be traced to the animal product by positive culture.

ARRHYTHMIA

An alteration of the heart's rhythm from normal sinus rhythm which requires drug and/or pacemaker therapy.

BLEEDING

Extravascular blood loss requiring volume replacement of surgical interventions

BLEEDING EVENT

Any episode of major internal or external bleeding that causes death, hospitalization, or permanent injury (e.g., vision loss) or requires transfusion. The complication "bleeding event" applies to all patients, whether or not they are taking anticoagulants or antiplatelet drugs, because bleeding events can occur in patients who are not anticoagulated.

CARDIAC ARREST

Permanent or temporary cessation of organized heart function, or precipitous drop in blood pressure sufficiently severe to require cardiopulmonary resuscitation (CPR) or emergency defibrillation.

CAROTID ARTERY STENOSIS (CAS) GRADE

Mild: Amaurosis fugax

Moderate: TIA/minor stroke

Major: Major stroke

COMPLICATION

An undesirable or unexplained clinical event experienced by the patient that results in death, injury, or invasive intervention. Complications may or may not be related to the bypass conduit.

EARLY MORTALITY

Any mortality that occurs within the first 30 days postoperatively.

ELECTRONIC CASE REPORT FORM (eCRF)

An electronic form designed to record protocol required information that is to be reported to the Sponsor on a clinical study patient.

EXPLANT

Removal of the study device for any reason.

FDA

Food and Drug Administration

HEART FAILURE

An event in which the heart fails to meet the circulatory requirements of the body under differing physiological circumstances, and/or a state in which cardiac output is reduced relative to the metabolic demands of the body, assuming the evidence of adequate venous return.

INFECTION

Bacterial or fungal proliferation confirmed by organism culture or systemic or localized reaction.

INFORMED CONSENT

A written document that contains relevant information about the clinical study and that is signed and dated by the patient or the patient's legally acceptable representative.

INSTITUTIONAL REVIEW BOARD (IRB)

An independent body consisting of medical professionals and nonmedical members responsible for reviewing and providing initial and continuing approval of research in human patients and verifying that the safety, integrity, and human rights of patients participating in a particular clinical study are protected.

MORTALITY

Permanent cessation of all vital bodily functions.

MYOCARDIAL INFARCTION

An area of coagulation necrosis resulting from impaired oxygenation of the myocardium. Events that are excluded are those patients who possess normal coronary arteries or if the patient is less than 40 years of age (will be reported as embolism events).

NEW YORK HEART ASSOCIATION CLASSIFICATION (NYHA)

Classification system used to categorize a patient's symptoms of heart failure.

NSAID

Nonsteroidal anti-inflammatory drug.

NYHA CLASS I

Patients with cardiac disease but without resulting limitations of physical activity. Ordinary physical activity does not cause undue fatigue, palpitation, dyspnea, or angina pain.

NYHA CLASS II

Patients with cardiac disease resulting in slight limitation of physical activity. They are comfortable at rest. Ordinary physical activity results in fatigue, palpitation, dyspnea, or anginal pain.

NYHA CLASS III

Patients with cardiac disease resulting in marked limitation of physical activity. They are comfortable at rest. Less than ordinary physical activity causes fatigue, palpitation, dyspnea, or anginal pain.

NYHA CLASS IV

Patient with cardiac disease resulting in inability to carry on any physical activity without discomfort. Symptoms of cardiac insufficiency or of the anginal syndrome may be present even at rest. If any physical activity is undertaken, discomfort is increased.

PRINCIPAL INVESTIGATOR

An individual responsible for the conduct of the clinical investigation at a study site. In the event the study is conducted by a team of individuals at a study site, the Principal Investigator is the responsible leader of the team.

REOPERATION

Any operation that repairs, alters, or replaces PhotoFix and/or the surrounding tissue.

RUTHERFORD CLASSIFICATION FOR CHRONIC LIMB ISCHEMIA

Category 0: Asymptomatic—no hemodynamically significant occlusive disease

Category 1: Mild claudication

Category 2: Moderate claudication

Category 3: Severe claudication

Category 4: Ischemic rest pain

Category 5: Minor tissue loss—nonhealing ulcer, focal gangrene with diffuse pedal ischemia

Category 6: Major tissue loss—extending above transmetatarsal level, functional foot no longer salvageable

SERIOUS ADVERSE EVENT (SAE)

A serious adverse event (experience) or reaction is any untoward medical occurrence that at any dose: results in death, is life-threatening, requires inpatient hospitalization or prolongation of existing hospitalization, results in persistent or significant disability/incapacity, or is a congenital anomaly/birth defect.

SPONSOR

An individual, device company, governmental agency, academic institution, private organization, or organization that takes responsibility for and initiates a clinical investigation.

SUDDEN UNEXPECTED, UNEXPLAINED DEATH

The cause of these deaths is unknown and the relationship to a bypass conduit is also unknown. These deaths should be reported as a separate category of bypass mortality if the cause cannot be determined by clinical data or autopsy.

THIRTY-DAY MORTALITY

Thirty-day Mortality (sometimes termed Operative Mortality) is death within 30 days of operation regardless of the patient's geographic location. Hospital Mortality is any death within

any time interval after operation if the patient is not discharged from the hospital. (Hospital-to-hospital transfer is not considered discharge; transfer to a nursing home or rehabilitation unit is considered hospital discharge unless the patient subsequently dies of complications of the operation.)

UNANTICIPATED ADVERSE EFFECTS (UAEs)

Any serious adverse effect on health or safety or any life-threatening problem or death caused by, or associated with, a product, if that effect, problem, or death was not previously identified in nature, severity, or degree of incidence in the study protocol, or any other unanticipated serious problems associated with a product that relates to the rights, safety, or welfare of a Patient.

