3.3 Study Population

Candidates for this study are adults who require vascular repair or reconstruction surgery that necessitates the use of a patch. Examples of vascular procedures include the repair and reconstruction of the carotid, iliac, femoral, and tibial blood vessels, as well as arteriovenous access procedures.

Study patients will be evaluated by medical history, disease process, and anatomic suitability for the study. To be enrolled in the study, candidates must meet the following Inclusion and Exclusion Criteria.

3.3.1 *Inclusion Criteria:*

- Patient is undergoing a vascular procedure which falls within the indications for use and requires the use of PhotoFix Decellularized Bovine Pericardium
- Patient's surgery is anticipated to occur within 60 days of consent
- Patient is ≥ 18 years old
- Patient is willing and able to comply with the protocol and follow up period
- Patient is willing and able to give written informed consent

3.3.2 *Exclusion Criteria:*

- Patient's procedure is a revision of a prior arteriotomy or venotomy
- Patient's procedure requires multiple vascular patches in anatomically distinct regions or other prosthetics (e.g. stents)
- Patient has a medical history of abnormal coagulopathy, bleeding, or thromboembolic disease
- Patient has a medical history of severe immunodeficiency disease
- Patient has a medical history of cancer
- Patient has severe visceral disease in heart or active liver disease or icterus
- Patient has a history of cerebrovascular accident (completed stroke) within 3 months of planned surgery
- Patient has a history of atrial fibrillation and requires a patch for carotid endarterectomy repair
- Patient has an active or potential infection at the surgical site
- Patient has used or plans to use immunomodulatory drugs for ≥ 6 months
- Patient has a sensitivity to products of bovine origin
- Patient is currently enrolled in another study
- Patient has a life expectancy of less than 12 months
- Patient is pregnant or breastfeeding or planning on becoming pregnant or unwilling to use medically acceptable methods of birth control
- Patient's procedure is emergent

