7. History of Hypertension	 None (cutoff point, diastolic pressure usually lower than 90 mm Hg)  Controlled (cutoff point, diastolic pressure usually lower than 90 mm Hg) with single drug  Controlled with two drugs  Requires more than two drugs or is uncontrolled  Unknown
8. History of Hyperlipidemia	 Cholesterol (low-density lipoprotein and total) and triglyceride levels within normal limits for age  Mild elevation, readily controllable by diet  Moderate elevation requiring strict dietary control  Moderate elevation but severe enough to require dietary and drug control  Unknown
9. History of Diabetes	 None  Adult onset, controlled by diet or oral agents  Adult onset, insulin-controlled  Juvenile onset  Unknown
10. History of Coronary Artery Disease	 Yes  No  Unknown
11. History of Congestive Heart Failure *Refer to Appendix E: Definitions and Acronyms	 None  NYHA Class I  NYHA Class II  NYHA Class III  NYHA Class IV  Unknown
12. History of Myocardial Infarction *Refer to Appendix E: Definitions and Acronyms	 None  Recent, < 4 weeks

Medical History eCRF	
	 Past, \geq 4 weeks  Unknown
13. History of Renal Insufficiency	 No known renal disease, normal serum creatinine level  Moderately elevated creatinine level, as high as 2.4 mg/dL  Creatinine level, 2.5 to 5.9 mg/dL  Creatinine level greater than 6.0 mg/dL, or on dialysis or with kidney transplant  Unknown
14. History of Stroke	 0  1  2  3  \geq 4  Unknown
If \geq 1, indicate when the most recent stroke occurred.	/ / Month/Day/Year

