5. Classify the event as one of the following (if multiple symptoms, classify by most severe)	 Amaurosis Fugax  Bleeding event  Cardiac event  Endoleak  Infection  Inflammation/Edema  Pain  Paraparesis  Renal event  Stroke  Symptomatic Carotid Occlusion  Thrombosis  Trauma  Transient Ischemic Attack  Other: _____
(Infection only), was a culture taken?	 Yes  No
(Infection only), If yes, what were the reported results?	 Inconclusive  Positive (identify organisms): _____  Negative  Report not available
6. Describe the Event	
7. Consequence of Adverse Event	 Surgical Intervention  Hospitalization (New or Prolonged)  Death  Other: _____  None

*Select all that apply

Adverse Event eCRF	
If death is indicated, provide cause of death	 Unknown
8. Required Drug Treatment *Update Medication eCRF, as applicable	 Yes  No  Unknown
9. Classify the Adverse Event. *Refer to Protocol Appendix E, Definitions	 Adverse Event (AE)  Unanticipated Adverse Effects (UAE)  Serious Adverse Event (SAE)
If SAE, select at least one of the following	 Death  Life Threatening  Other Medically Important Serious Event  Persistent/ Significant Disability  Requires or Prolongs Hospitalization *Select all that apply
10. Is the event related to the subject's vascular surgery?	 Yes  No
11. Is the Adverse Event related to PhotoFix?	 Definitely  Probably  Possibly  Unrelated

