## **2.17. Adverse Events**

Adverse events will not be coded. The incidence of adverse events will be summarized for the aggregate sample. Adverse events will be considered as any event happening during or after PhotoFix implant. Any adverse event that occurs prior to surgery will not be included in the summary or analysis.

Adverse events will be summarized based on timing, in relation to surgery. Events will be categorized as early if the event occurs  $< 30$  days after surgery, while late post-operative events will be considered as events occurring  $\geq 30$  days after surgery.

Adverse events will be summarized by pre-specified category; events classified as other will be manually classified, as deemed appropriate. The following will be included in the summary of adverse events: consequence of event, required drug treatment or intervention, severity, relation to surgery, relation to PhotoFix, and status of event at end of study. Events deemed to be related to PhotoFix, with any definitive assessment, will be summarized in a frequency table; additional information discovered during event investigation will be described, as deemed necessary.

Adverse event rate will be presented as frequency counts and percentages in a table for enrolled patients. Adverse events will be presented in aggregate and by surgical indication.

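### The myocardial infarction definition drops infarctions under age 40 or with normal coronary arteries and sends them to an embolism label the forms lack, so baseline history may be under-counted and event categories may differ between sites

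*Protocol*

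**What the plan says.** Appendix E of the protocol describes myocardial infarction as necrosis from impaired oxygenation of the heart muscle. Its second sentence takes some cases out: "Events that are excluded are those patients who possess normal coronary arteries or if the patient is less than 40 years of age". A parenthesis at the end of that sentence says they "will be reported as embolism events". The grammar leaves open whether the parenthesis covers both exclusions or only the age one.

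Three other places bear on this rule:

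- **Eligibility (Protocol 3.3.1).** The age criterion is "Patient is ≥ 18 years old", so patients aged 18 to 39 can be enrolled.
- **Forms (Protocol Appendix D).** Item 5 of the Adverse Event form instructs sites: "Classify the event as one of the following (if multiple symptoms, classify by most severe". Its options include "Cardiac event", thrombosis and other. Item 12 of the Medical History form, "History of Myocardial Infarction", carries a note sending the site to Appendix E.
- **Analysis (SAP 2.17).** Adverse events are summarised by the categories on the form, and "events classified as other will be manually classified, as deemed appropriate".

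**The concern.** The definition gives an instruction that the Adverse Event form cannot carry out. A site told to report an infarction as an embolism finds no such option and no definition of the term. It must either ignore Appendix E and use the cardiac option, or follow Appendix E and use *Other*. The row in which the event appears then depends on who read the appendix, and later on how the sponsor classifies the *Other* entries.

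The baseline consequence is more direct, because the Medical History item explicitly relies on Appendix E. A site applying the definition as written could answer that there is no history of infarction for a patient who has had one. Protocol 6.7 plans to describe comorbidities at baseline, so this would make the cohort look slightly healthier than it is. Also at stake is the adverse event table by category, which SAP 2.17 presents in aggregate and by surgical indication.

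**Working it through.** The plan states no figure on this point, so there is none to reproduce. The check sets the texts side by side and then gives a sense of scale.

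**Step 1. Does the destination exist?** Item 5 of the Adverse Event form has 15 options: amaurosis fugax, bleeding, cardiac, endoleak, infection, inflammation/edema, pain, paraparesis, renal, stroke, symptomatic carotid occlusion, thrombosis, trauma, transient ischemic attack and other. None is embolism and none is myocardial infarction. In Appendix E, embolism appears only inside the infarction definition.

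**Step 2. What can a site do with an excluded infarction on study?** Item 5 carries no reference to Appendix E; on that form the reference is at item 9, which sorts events into AE, UAE and SAE. Two entries are therefore defensible:

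- *Cardiac option:* the event stays in the cardiac row.
- *Other:* the event goes to manual classification under SAP 2.17, where an embolism label is possible but not required.

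**Step 3. Can the rule be applied evenly?** One branch needs the state of the coronary arteries. The Imaging form concerns the target vessel, and Protocol 1.2 requires no study-specific imaging. The Medical History form asks only whether there is a history of coronary artery disease. The branch can operate only where routine care happens to have shown the coronary arteries.

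**Step 4. What happens at baseline?** Item 12 offers none, recent (under 4 weeks), past (4 weeks or more) and unknown. There is no embolism answer, so a prior infarction that fails the definition most naturally becomes *None*. The item asks for no date, unlike the stroke and TIA items on the same form, so age at the infarction cannot be recovered from it. Each patient recorded this way lowers the baseline percentage by 1/100, or 1 percentage point, in a cohort of 100. The documents give no basis for estimating how many there would be.

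**Step 5. Which results depend on the category?** The CEA primary endpoint counts TIA, amaurosis fugax, stroke and symptomatic carotid occlusion. The non-CEA primary endpoint is patency. The adverse event rate in SAP 2.9.2 is the percentage of patients with at least one event, or at least one device-related event. None of these changes when an infarction moves between the cardiac option and *Other*. No infarction or embolism endpoint is listed in Protocol 6.1 or SAP 2.9.

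**Step 6. Scale of the on-study effect.** N = 100 comes from Protocol 3.2 and SAP 2.20. The infarction rate r and the share s of infarctions meeting the exclusion are assumptions, not document figures.

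Expected events = N × r × s. Chance of at least one = 1 − (1 − r × s)^N.

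| r | s | Expected events | Chance of at least one |
|---|---|---|---|
| 1% | 5% | 100 × 0.01 × 0.05 = 0.05 | 1 − 0.9995^100 = 0.049 |
| 3% | 15% | 100 × 0.03 × 0.15 = 0.45 | 1 − 0.9955^100 = 0.363 |
| 5% | 25% | 100 × 0.05 × 0.25 = 1.25 | 1 − 0.9875^100 = 0.716 |

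**The case against.** A reader might infer that the rule systematically removes infarctions from the cardiac count and builds a misleading embolic count that looks like a signal from the patch. The documents do not support that:

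- No embolism count is planned. An embolism row could arise only if a site chose *Other* and the sponsor then assigned that label by hand.
- Appendix E narrows the term myocardial infarction. It does not narrow the form's cardiac category, so a site may tick that option for every infarction.
- Relation to PhotoFix is a separate item (11) on the Adverse Event form, and SAP 2.17 lists it separately from category. An embolism label would not by itself make an event device-related.
- The definition names no source of embolism, so it does not show that the patch is presumed to shed emboli into the coronary arteries. An argument from implant site is also weak: Protocol 2.8 gives the vessels as examples, and the Medical History form also lists the thoracic aorta.
- If the parenthesis covers only the age clause, an older patient with normal coronary arteries falls outside the definition but is not assigned to embolism.

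There are also safeguards. The form requires a free-text description, SAP 2.1 and 2.21 provide listings of all data, and Protocol 7 intends full source verification. Baseline history is summarised only descriptively, and no eligibility criterion or model uses item 12.

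All of this stands, and it limits the point to inconsistent categories and a possible baseline under-count. It does not remove the mismatch between definition and form. Nor does source verification clearly protect item 12: a monitor applying the same Appendix E definition could accept *None* as correct.

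**Conclusion.** The definition is wrong as written, and the consequence is minor. It contains an explicit exclusion with a destination that the Adverse Event form does not offer and Appendix E does not define. The firmer consequence is at baseline, where item 12 relies on the definition and a true prior infarction could be recorded as *None*. The other is that similar on-study infarctions could be categorised differently from site to site.

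Under the assumed rates, about 0.05 to 1.25 on-study events per 100 patients are involved, with a 5% to 72% chance of at least one. These figures count infarctions that meet the exclusion; fewer would be categorised differently if most sites use the cardiac option. The size of the baseline effect cannot be estimated from the documents. The primary endpoints, the listed secondary endpoints and the any-event percentage are unaffected.

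**What to change.** 1. In Appendix E, delete the second sentence of the myocardial infarction definition, including the embolism parenthesis. Medical History item 12 then uses the definition without the exclusion.
2. State in Appendix E or beside item 5 of the Adverse Event form that a myocardial infarction is classified under the cardiac category. Deleting the sentence is not enough, because nothing on the form now links infarction to that option.
3. Record an embolism only when one is documented.

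The cost is one deleted sentence and one added line. No new data or analysis is needed. If sites have already completed item 12, the *None* answers should be queried against source records, since the form holds no date from which to correct them.

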APPENDIX G: PROTOCOL DEVIATION REPORT FORM

PROTOCOL DEVIATION/WAIVER FORM

Please E-mail this form to: [contact]

To: _____
From: _____
Investigator Name: _____ Phone: _____
Site/Center Number: _____ Fax: _____

Study Name:	PHOTO-V			
Protocol Number:	PHF1801.000-M (04/18)			
Patient Initials:		Patient #:		Visit Date & Visit #:

All deviations from the protocol that are related to study inclusion or exclusion criteria, conduct of the study, subject management, or subject assessment must be reported using this form.

Investigator's Reason for Deviation:

Please provide a brief summary of the request in the space provided.

Summary: _____

By signing this request you agree that if the deviation occurs the following conditions remain satisfied:

- The patient's safety is not jeopardized by continuing in the study; and,
- In your opinion, the protocol objectives are not compromised.

PI Signature:		Date:	/	/
---------------	--	-------	---	---

Acknowledgement				
CryoLife Signature:		Date:	/	/

**Revision History**

Version Date	File Name	Summary of Changes
07/27/2018	PHOTO-V Study Statistical Analysis Plan V1.0	Initial Version

## 1. INTRODUCTION

### 1.1. Scope

This document contains detailed information to aid in the production of the Interim Analysis Report and the Final Study Report for the *PHOTO-V* Study. The contents of this document were written and reviewed by the sponsor, CryoLife, Inc.

### 1.2. Study Overview

This study is a post-market, prospective, multicenter study designed to evaluate the clinical outcomes of patients receiving PhotoFix® Decellularized Bovine Pericardium (PhotoFix) as a patch within a vascular repair or reconstruction procedure. A goal of 100 patients will be enrolled at approximately 10 sites.

The primary study endpoint for patients with carotid artery stenosis (CAS) undergoing carotid endarterectomies (CEA) will be rate of ipsilateral central neurologic events; the primary endpoint for all other vascular procedures will be primary patency. The secondary endpoints include overall survival, all-cause reoperation rate, device-related reoperation rate, explant rate, restenosis rate, adverse event rate, and secondary patency (hemodialysis access repair (HAR) only). Data will be collected at 5-time points: baseline (pre-operatively), intra-operatively, 1 month post-operatively, 3 months post-operatively, and 6 months post-operatively.

The investigation will be conducted for a period of time required to collect all follow-up, as needed on each patient, but no longer than 7 months after the patient's operation.

